### **6.5 CONCOMITANT THERAPY**

Antibiotics are excluded from this trial. However, any other prescription medication is defined as a medication that can be prescribed by a properly authorized/licensed clinician is allowable.

Medications will be reported in the Case Report Form (CRF) as concomitant prescription medication, including over-the-counter medications and supplements.

## **7 STUDY INTERVENTION DISCONTINUATION AND PARTICIPANT DISCONTINUATION/WITHDRAWAL**

### **7.1 DISCONTINUATION OF STUDY INTERVENTION**

Participant will be discontinued from participation in study if:

- Completion of study trial
- If any clinical adverse event (AE), laboratory abnormality, or other medical condition or situation occurs such that continued participation in the study would not be in the best interest of the participant
- Positive pregnancy test
- Participant unable to receive study intervention for two consecutive days.

Any clinically relevant finding will be reported as an AE. All study related indices will be recorded and maintained up to the time of discontinuation. Clinical staff will also follow-up with participant to capture AE, serious adverse events (SAE), and unanticipated problems (UPs)

### **7.2 PARTICIPANT DISCONTINUATION/WITHDRAWAL FROM THE STUDY**

Participants are free to withdraw from participation in the study at any time upon request, or upon the development of an adverse reaction due to exposure to intervention.

PI may discontinue or withdraw participant from the study for the following reasons:

- Significant study intervention non-compliance
- If the participant meets an exclusion criterion (either newly developed or not previously recognized) that precludes further study participation
- Death
- Screen failure

The reason for participant discontinuation or withdrawal from the study will be recorded on the ‘Current Status’ CRF. Subjects who sign the informed consent form and are randomized and receive the study intervention and subsequently withdraw or are withdrawn or discontinued from the study will be replaced. Prior to removal from study, efforts will be made to have participant complete a safety visit approximately one week following the last dose of study product.

### **7.3 LOST TO FOLLOW-UP**

A participant will be considered lost to follow-up if he or she fails to return for the three subsequent scheduled visits following baseline visit and is unable to be contacted by the study GENE-FORECAST-SIT staff .

The following actions will be taken if a participant fails to return to the clinic for a required study visit:

- The GENE-FORECAST-SIT staff will attempt to contact the participant and reschedule the missed visit one week and counsel the participant on the importance of maintaining the assigned visit schedule and ascertain if the participant wishes to and/or should continue in the study.

- Before a participant is deemed lost to follow-up, the GENE-Forecast-SIT staff will make every effort to regain contact with the participant (where possible, 3 telephone calls and, if necessary, a certified letter to the participant's last known mailing address or local equivalent methods). These contact attempts will be documented in the participant's medical record or study file.
- Should the participant continue to be unreachable, he or she will be considered to have withdrawn from the study with a primary reason of lost to follow-up.

## 8 STUDY ASSESSMENTS AND PROCEDURES

### 8.1 SCREENING PROCEDURES

A listing of former normotensive GENE-Forecast participants will be generated, including those in the upper tertile with vascular stiffness, by the data base manager that consented for re-contact via the 'Call Back' protocol. The Research Nurse will contact individual to determine interest in participating in GENE-Forecast-SIT and screen via the telephone for eligibility based on self-reported health information. Participant who agree to participate in study will be scheduled for baseline clinical visit based on availability and subsequently screened again at the Clinical Center. All participants will undergo screening activities upon coming to the NIH. Female participants will undergo a pregnancy test after consent signature. Participants who consent to participate in the trial and subsequently have a positive pregnancy test prior to randomization will be considered a screen failure and not enrolled in the study.

### 8.2 EFFICACY ASSESSMENTS

1. Salt/Placebo Intervention: Capsules will be dispensed by Clinical Center Pharmacy.
2. Flow Activating Cell Sorting (FACS) Analysis: Characterization of Leukocytes  
Populations : As part of assessing the whole blood epigenome and transcriptome, the protocol will perform an in-depth characterization of the heterogeneous mixture of leukocytes circulating in the blood and how this profile might be altered in response to the dietary sodium intervention. We will utilize the NHLBI's Flow Cytometry Core in collaboration with [name]. We will collect peripheral blood samples at the 4 time points (visit 1, 2 3 and 4). The FACS analysis will define changes in immune cell-type profiles as well as facilitate the isolation of DNA/RNA from specific immune cell sub-types (e.g. CD4 T-cells; CD8 T-cells, Monocytes etc.) for epigenome and transcriptome analysis.
3. Vascular function testing: These tests will be done using specialized non-invasive machines, such as SphygmoCor and EndoPAT, to assess vascular health.
4. 24-hour ambulatory blood pressure monitoring: Participants will be given an ambulatory blood pressure monitoring device that will be worn for 24 hours within two days of NIH baseline visit and again for 24 hours within two days prior to the return visits.
5. A 24-hour dietary recall will be administered at baseline and at each subsequent visit to assess differential diet and salt intake among each participant. Nutrition staff from the Clinical Center will meet with each participant and ask them to recall any foods or beverages they have eaten over the past 24 hours using an automated dietary analysis software application developed by the US Department of Agriculture for use in the National Health and Nutrition Examination Survey. The intakes for 108 nutrients (including salt) will be calculated for each participant based on individual diet.
6. Psychophysical Taste Task: Sucrose and Salt Detection Thresholds: Sucrose and salt detection thresholds will be assessed using a two-alternative forced-choice staircase procedure

was developed at the Monell Center for Adults. The two-alternative forced choice is a psychophysical method developed to elicit responses about an individual's experience regarding a stimulus. It focuses on the evaluation of a single attribute (e.g., sweetness or saltiness), and the stimulus is adjusted based on the individual's responses. For this study, all testing will take place in a private, comfortable room. Subjects will be fasted for at least one hour before the task and acclimate to the testing room and to the researcher for approximately 15 minutes before testing. For the first trial and each subsequent trial, subjects will be presented with pairs of solutions in random order; within each pair, one solution will be distilled water, and the other will be the taste stimulus. Subjects will be instructed to taste the first solution presented within the pair, swish the solution in their mouth for 5 seconds, and expectorate. This will be repeated for the second solution within the pair. Between solutions, subjects will rinse their mouth with water; they will rinse once within a pair, and twice between successive pairs. After tasting both solutions within a pair, subjects will be asked to point to the solution that has a non-neutral taste. A tracking grid will be used to record subjects' response. This method eliminates the need for a verbal response and has been shown to be an effective method for assessing both taste and olfaction in children. The task takes approximately 30 minutes to complete.

7. Psychophysical Taste Task: Sucrose and Salt Preference: Sucrose and salt preference will be assessed using a two-series paired comparison-tracking method developed at the Monell Center for Adults. Subjects will be presented with pairs of solutions differing in sucrose concentration (3, 6, 12, 24, and 36 g per 100 mL) and salt (0.92–6.14% wt/vol NaCl). They will be asked to taste the solutions without swallowing and point to which of the pair they liked better. Subsequently, each pair presented will be determined by the subject's preceding preference choice. The entire task is then repeated with the stimulus pairs presented in reverse order. After completion of the taste task, the geometric mean of the sucrose concentrations chosen will be determined. This serves as an estimate of the participant's most preferred level of sucrose. The task takes approximately 15 minutes to complete.

8. Baecke's Physical Activity Questionnaire: Physical activity will be assessed using 16 questions involving three habitual physical activities (occupational physical activity, physical exercise, and leisure activities) during the previous 12 months.

9. Pittsburgh Sleep Quality Index (PSQI): This is a 19-item self-rated questionnaire for evaluating subjective sleep quality over the previous month.

10. Microbiome: Skin, saliva and stool samples will be collected by the GENE-FORECAST-SIT staff based on the utilization of Norgen kits. Participant will be swabbed in three locations of the skin and will spit in a prepared vial. Subjects will be required to not shower within 12 hours of sampling based on the guidelines from the NIH common fund Human Microbiome Project, an initiative to generate resources and facilitate the characterization of the human microbiota (Human Microbiome Project, *Nature*, 2012). Stool kits will be previously mailed to participant for collection and participant will give stool sample to GENE-FORECAST-SIT staff at the clinic appointment.

It is estimated that participants will spend approximately 5 hours at the Clinical Center during baseline and approximately 3 hours during each of the subsequent visit. Obtaining and explaining the informed consent will take about 20-30 minutes. Female prospective participant who signs consent and subsequently test positive for pregnancy prior to randomization will not be enrolled in the study. Administering the baseline questionnaires will take about 1.45 hours and 75 minutes for the 24-hour diet recall and taste assessments for each subsequent visit. The clinic visit

assessment, plus vascular function test and microbiome collection, will take about 1.30 hours. A member of the clinical study staff will follow-up with participant one week after visit to assess any adverse reaction to consuming intervention product. All procedures and details for each can be found in the study's Manual of Operation (MOP).

**Table 1: Estimated length of time for study procedures**

NIH Clinic Visit	Estimated time 4 hours	Total Participants	Duration of Study
a) Informed consent (baseline only)	20-30 minutes	40	7 wks
b) Phlebotomy	30 minutes	40	7 wks
c) Physical examination	20 minutes	40	7 wks
d) Baseline Questionnaires: Baecke's Physical Activity Pittsburgh Sleep Quality Index	1.45 hours	40	Baseline
e) 24 diet recall	30 minutes	40	7wks
f) Psychophysical Taste Task: Sucrose and Salt Detection Thresholds	30 minutes	40	7 wks
g) Psychophysical Taste Task: Sucrose and Salt Preference	15 minutes	40	7 wks
h) Microbiome	15 minutes	40	7 weeks
i) Vascular Function	1.0 hrs	40	7 wks

### **8.2.1 Clinical Evaluations**

**Physical examination:** A physical examination will be performed by the study Physician Assistant to include health/medication history and measurements of height and weight. Vital signs including temperature, pulse, respirations, and blood pressure, will be also be collected.

### **Radiographic or other imaging assessments:**

Radiology or other imaging will not be conducted in this study.

### **8.2.2 Biospecimen Evaluations**

Participants will undergo standardized blood collection for chemistry panel, blood pressure measurement and vascular function test. Biological specimens will include peripheral venous blood collected by phlebotomy, urine, and stool. All biospecimens will be collected at the NIH Clinical Center which is in compliance with Clinical Laboratory Improvement Amendments

(CLIA). Blood, urine and stool samples will be collected from the Clinical Center by the GENE-FORECAST-SIT staff. The samples are brought to PI's lab by research study lab assistants where Laboratory Manager will prepare and store samples in freezers. Shipment of blood and microbiome samples for each visit per participant will be sent overnight for assay in dry ice in compliance with standard procedures. Each sample will be labelled with participant study ID.

Urine sample: (small quantity, 1 cup 90 ml)

1. Urine chemistries (e.g. sodium, chloride, potassium)
2. Urine creatinine and microalbumin (ACR)
3. Urine protein to creatinine ratio (PCR)
  1. Osmolality
  2. Urea Nitrogen
  3. Urine exosomes (RNA/microRNA)

Microbiome samples:

Stool/At home collection kit (quantity = 2 grams):

Skin: swab of inner elbow and behind ears

Oral: saliva

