**Table 2: Specific activities by visit**

Activity	Visit 1 (baseline)	Visit 2 (after 2-week treatment)	Visit 3 (after 3-week washout)	Visit 4 (after second 2-week treatment)
24-Hour nutrient recall	x	x	x	x

Psychophysical Taste Task: Sucrose and Salt Detection Thresholds	x	x	x	x
Psychophysical Taste Task: Sucrose and Salt Preference	x	x	x	x
History and physical exam with medication history	x	x	x	x
Baeke's physical activity questionnaire	x			
Pittsburg sleep questionnaire	x			
Stool/skin/mouth swabs for microbiome analysis	x	x	x	x
Urine sample	x	x	x	x
Blood sample	x	x	x	x
Vascular function	x	x	x	x
24-hour blood pressure monitor given to participant	x		x	
24-hour blood pressure monitor returned by participant		x		x

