**4.2 SCIENTIFIC RATIONALE FOR STUDY DESIGN**

The study is testing the hypothesis that a modest increase in dietary sodium intake is sufficient to change the gut microbiome and trigger alterations in the blood transcriptome that may mediate the resultant in the well described salt-sensitive changes in vascular function, epigenome, transcriptome and blood pressure observed in African Americans. The study design as a randomized, double-blind, placebo-control cross-over design enables each participant to serve as her/his own control in response to the dietary salt intervention. The cross-over design allows for an intervening ‘wash-out’ period to ensure that the participant’s diet and sodium homeostasis returns to baseline. The design’s use of each participant as her/his own control reduces the impact of inter-individual variability in the basal dietary habits and microbiome; and optimizes statistical power to detect differences in baseline blood transcriptome gene expression profiles and gut microbiome in response to the dietary intervention. Our previous studies of the human transcriptome indicate that the current design is very robust to detect changes in gene expression by DNA methylation, RNA-seq and vascular function. The randomization ensures that the sequence order of the intervention (placebo vs salt tablets) is due to chance and avoids a systematic ‘contamination’ or carryover effect of the active treatment. The double-blind administration of tasteless capsules ensures that neither the participant or research staff are aware that there could be an increased ingestion of dietary salt. The dose of sodium chloride in the capsule has previously been shown to affect biomarkers sensitive to salt balance such as measures of the renin-angiotensin-aldosterone system and blood pressure. The daily dose of sodium chloride tablets given in the protocol falls well within the wide variance of ‘normal’,

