**Microbiome:**

BODY SITE	SPECIMEN	COLLECTION TUBE
Oral Cavity	Saliva	Saliva DNA Collection, Preservation, and Isolation Kit
Skin	Retroauricular Crease (Left)	Swab Collection and DNA System
	Retroauricular Crease (Right)	
	Antecubital Fossa (Left)	
	Antecubital Fossa (Right)	
GI Tract	Stool	Norgen Stool Nucleic Acid Collection and Preservation System

Total volume of blood collected per visit = 87 ml, which is equivalent to about 5.8-6 tablespoons of blood.

Biological specimens collected from individuals will include peripheral venous blood and urine samples collected by phlebotomy. Oral microbiome samples will be acquired using a spit collection kit. Skin swabs will be used to obtain skin microbiome samples from the left and

right retroarticular crease, as well as, the left and right antecubital fossa. Stool microbiome samples will be collected in a stool kit mailed to participants prior to clinic visit. Detailed instructions for the preparation, handling, storage, and shipment of specimens will be explained in the study's MOP.

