**Laboratory evaluations:**

DNA and RNA extractions will be done by ReproCELL USA, Inc. DNA and RNA sequencing will be done by the NIH Intramural Sequencing Center (NISC). Microbiome assay will be done by University of Pennsylvania Microbiome Center. Flow Activating Flow Cell Sorting (FACS) Analysis will be conducted by the NHLBI's Flow Cytometry Core in collaboration with [name].

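### Samples go out for assay visit by visit with no same-run or batch-recording rule, so batch variation can cost precision in the salt–placebo contrast for microbiome, methylation and whole-blood RNA-seq

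*Combined protocol and SAP*

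**What the plan says.** Blood, urine and microbiome samples are collected at all four visits (Table 2). The two end-of-treatment samples come from Visits 2 and 4. These are five weeks apart: a three-week washout plus the two-week second period (Section 4.1).

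On handling, Section 8.2.2 first says that the "Laboratory Manager will prepare and store samples in freezers", for a time not stated. It then says: "Shipment of blood and microbiome samples for each visit per participant will be sent overnight for assay in dry ice". The end of the same section adds: "Detailed instructions for the preparation, handling, storage, and shipment of specimens will be explained in the study's MOP". The manual of procedures (MOP) is not among the documents.

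The Laboratory evaluations paragraph gives extraction to one outside laboratory ("DNA and RNA extractions will be done by ReproCELL USA, Inc"), sequencing to an NIH sequencing centre, and the microbiome to another ("Microbiome assay will be done by University of Pennsylvania Microbiome Center"). It does not say how any of them groups samples into extraction, library or sequencing runs.

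The analysis sections name no batch term:
- **Microbiome (9.4.2):** treatment is the only covariate.
- **Methylation (9.4.3):** a two-sample t-test.
- **RNA-seq (9.4.3):** a negative binomial model with no batch term described.
- **Mixed model (9.2):** subject, period, sequence and carryover, but not batch. Microbiome is not among its outcomes.

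**The concern.** Section 4.2 justifies the crossover on the ground that own-control comparison "reduces the impact of inter-individual variability in the basal dietary habits and microbiome". Pairing removes whatever the two samples share. It removes assay variation only if both samples pass through the same run. If the Visit 2 and Visit 4 samples are processed as they arrive, differences in extraction kit, library preparation and sequencing run are added to each participant's salt-minus-placebo difference. The plan neither prevents this nor adjusts for it. At stake is the precision of one of the two primary endpoints and of two secondary endpoints, in a trial of about 28 to 40 people.

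**Working it through.** **The plan's own figure.** Section 9.2 assumes a PWV difference of 0.6 m/s, SD 0.9 m/s, within-subject correlation 0.3, 80% power and a two-sided 5% level.
- SD of the difference = 0.9 × √(2 × (1 − 0.3)) = 1.065 m/s.
- A paired t-test (noncentral t) needs 27 participants; with 28 the power is 82.0%. The stated 28 is reproduced within rounding.
- For dropout, 28 × 1.2 = 33.6, or 34; 28 / 0.8 = 35. The stated 34 is close enough.

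PWV is measured on the participant and is not shipped, so neither figure changes.

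**Effect on a paired comparison of a shipped endpoint.** Let f be the batch variance divided by the within-person residual variance σ². The documents give no value, so f is assumed. If the two samples fall in different, independent batches:
- Var(salt − placebo) = 2σ²(1 + f)
- standard error ratio = √(1 + f)
- effective pairs = 28 / (1 + f)

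The power column starts from a paired comparison with 80% power at 28 pairs and divides its noncentrality by √(1 + f).

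| f | SE ratio | Effective pairs out of 28 | Power |
|---|---|---|---|
| 0 | 1.00 | 28 | 80% |
| 0.25 | 1.12 | 22.4 | 71% |
| 0.5 | 1.22 | 18.7 | 63% |
| 1.0 | 1.41 | 14 | 51% |

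If both samples share a batch, the term cancels and power stays at 80%.

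**The same loss on another scale.** Suppose batch variance is 5% to 20% of the variance of a single measurement. Dividing by (1 − correlation) gives f:
- correlation 0.3: f = 0.05/0.7 = 0.07 to 0.20/0.7 = 0.29; power 77% to 70%
- correlation 0.7: f = 0.05/0.3 = 0.17 to 0.20/0.3 = 0.67; power 74% to 58%

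**Effect on the unpaired tests actually planned.** The estimated standard error there rests on total variance, so its ratio is √(1 + (1 − correlation) × f). At correlation 0.3 (borrowed from the PWV calculation) and f = 0.25 this is √1.175 = 1.08. Running a participant's samples together does not remove the term, because batch differences between participants stay in the residual. In simulation the unpaired test gained almost nothing from same-run assay.

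**Type I error.** Null simulations used 28 participants, correlation 0.3 and f of 0.25 or 1.0. Samples shared 2, 4 or 10 calendar batches, or all Visit 2 samples were in one batch and all Visit 4 samples in another. Order was randomised, simply or in balance. At the nominal 5% level the paired t-test rejected in 2.0% to 5.0% of runs and the two-sample t-test in 1.1% to 4.6%. The count models were not simulated.

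**The case against.** **A shipment is not an assay batch.** This is the strongest objection, and it stands. A laboratory may hold frozen samples and run a participant's set together. Sequencing takes place at a different centre from extraction, so its runs are not set by these consignments. The shipment sentence follows a freezer step of unstated length and may describe what is packed rather than when it is sent. The MOP may already settle the matter. A reader might infer that batch variation does enter the within-person contrast; the documents support only that it can.

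**Correlated errors and p-values.** A reader might also infer that participants sharing a batch have correlated errors, so that p-values come out too small. That does not follow. Order is randomised per participant (Section 6.3), so a shared shift enters each salt-minus-placebo difference with a random sign. The simulations show no inflation. The allocation ratio and blocking are not stated, and the microbiome and methylation analyses name no period term, so a chance imbalance in order could leave part of a visit-linked shift in one trial's estimate. Over the randomisation that is noise, not bias.

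**Split recruitment.** The addendum (Section 12) reports 20 participants and then 8 more. It is tempting to read this as making matters worse. The split lies between participants, while each person's visits fall within seven weeks, so it does not touch the within-person contrast.

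**Existing quality control.** The plan does include microbiome quality control, library-size and TMM normalisation, and methylation quality control. None of these is a batch adjustment.

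**Conclusion.** The point holds as a possible and avoidable loss of precision. The protocol's stated rule is shipment for assay by participant and visit. It has no same-run requirement, no instruction to record batch, and no batch term. The affected endpoints are the microbiome, methylation and whole-blood RNA-seq. PWV and blood pressure are not affected, and urine is not named in the shipment sentence.

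The size is unknown because the batch variance is unknown. The 12% to 41% increase in standard error rests on three assumptions: a paired analysis, independent batches for the two samples, and f between 0.25 and 1.0. If the laboratories already run each participant's visits together, the batch term cancels from the paired contrast. Even then, the unpaired tests in Sections 9.4.2 and 9.4.3 would not realise the benefit. This is a worthwhile, low-cost improvement and not a threat to validity.

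**What to change.** 1. **Shipment rule.** Amend Section 8.2.2 and the MOP so that frozen samples for DNA, RNA and microbiome assay are held until the participant's last visit. All of that participant's samples are then extracted, prepared and sequenced in the same run, with positions randomised and laboratory staff blind to visit.
2. **Exemption.** Exempt assays that cannot wait, such as FACS, and record their batch.
3. **Analysis.** Analyse these endpoints within participant, for example with a subject term or paired differences. Without this, same-run assay gains almost nothing.
4. **Samples already assayed.** The addendum counts 28 participants already enrolled, so holding may come too late for some. For these, obtain the extraction, library and sequencing run identifiers and include batch in the models. Batch can be separated from treatment only where runs contain both salt and placebo samples. Section 10.4 says residual specimens are not kept after completion, so a later re-run may not be possible.

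The cost is a change of wording, up to about 7 weeks more storage in freezers already in use, and no early look at sample quality. There would be fewer shipments. If the MOP already requires same-run assay, one sentence in the protocol settles the first item; the within-participant analysis is still needed.
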